#### 8.8.5 ECGs

Screening data collected on ECG (normal/abnormal) will be listed by patient number.

#### 8.8.6 Medication for Infusion Reaction

A by-subject listing will be provided by study part and treatment group for any medications to treat infusion reactions by ATC levels and PT on enrolled patients.

#### 8.8.7 MRI of Brain

Summaries of MRI scans will include:

- Number and percentage of patients with Screening scans classified as normal or abnormal
- For post-baseline scans: number and percentage of patients with scans classified as improved, worsened, or unchanged since previous scan, by visit
- Number and percentage of patients with any FLAIR lesions found, by visit
- Number and percentage of patients with any enhancing lesions found, by visit
- Number and percentage of patients with evidence of restricted diffusion present, by visit

By-subject listings of MRI findings also will be provided.

## 8.9 Efficacy Analysis

There is no efficacy analysis.

#### 8.10 Pharmacokinetics

Non-compartmental PK parameters will be determined using Phoenix® WinNonLin (WNL) version [8.3] or a later version in a secure and validated environment. All pharmacokinetic data analysis will be performed on the PKAS set.

#### 8.10.1 Pharmacokinetic Concentration Tables, Figures, and Listings

For Part A (SAD) and Part B (MAD), separately, plasma concentrations for ANK-700 will be summarized by treatment group, day of dose, and nominal protocol time point for PKAS. Additionally, Part A and B will be pooled for a combined summary concentration table by dose on the first (Day 1) dose only for PKAS.

A by-subject listing for plasma concentration data for ANK-700, will be listed by study part, treatment group, patient, and day/time of dose for PKAS. Listings will include nominal and protocol time, actual sampling time relative to start of infusion, actual infusion duration, scheduled infusion duration (30 minutes), and difference between scheduled and actual infusion duration.

All individual as well as summary concentration data (mean, SD, minimum, median, maximum, and geometric mean) will be reported in Table, Figures, and Listings to the same precision as the data provided by the Bioanalytical Lab, e.g, if concentrations are provided as 3 significant digits, TFLs will also report individual and summary concentration data as 3 significant digits. N will represent number of subjects in the treatment group, n will represent number of concentrations available at a nominal time, n(blq) will represent number of concentrations available at a nominal time that are blq, and n (ND) will represent number of concentrations available at a nominal time that were not drawn, not analyzed, or analyzed but not reportable. N and n's will be reported as whole number. Pharmacokinetic Parameters Tables, Figures, and Listings

Following figures will be presented for Part A and B, separately, and for Day 1 combined parts A and B (except for individual separate plots for each patient):

- Linear mean (+/- SD) plasma concentration-time profiles for ANK-700 (all doses on one plot)
- Semilogarithmic mean (+/- SD) plasma concentration-time profiles for ANK-700 (all doses on one plot)
- Linear individual concentration-time profiles for ANK-700 (all patients on same dose on one plot)
- Semilogarithmic individual concentration-time profiles for ANK-700 (all patients on same dose on one plot)
- Linear individual concentration-time profiles for ANK-700 (separate plot for each patient)
- Semilogarithmic individual concentration-time profiles for ANK-700 (separate plot for each patient)

#### 8.10.2 Pharmacokinetic Parameters Tables, Figures, and Listings

For Part A and Part B separately, and Part A and Part B, Day 1 (combined), summary tables of ANK-700 calculable pharmacokinetic parameters will be provided that were calculated using concentrations available in PKAS.

A by-subject listing for PK parameters for ANK-700 will be listed by study part, by treatment group, by patient and day of dose using the PKAS.

Following rules will be followed for reporting PK parameters:

For tmax, only median, minimum and maximum values will be presented.

For all other parameters N, n, mean, SD, CV%, median, minimum, maximum, geometric mean, and geometric CV% will be presented. N will represent the number of subjects in the treatment group and n will represent calculable PK parameter in the treatment group.

Lambda z dependent PK parameters, i.e.  $\lambda z$ ,  $AUC_{inf}$ , CL, Vz will not be summarized if  $r^2$ adjusted is <0.90, and/or span of the terminal phase is <1.3 times the half-life and/or the %extrapolation to calculate  $AUC_{inf}$  is >30%, unless otherwise determined by the PK scientist. Such parameters will be flagged in parameters listing, and if flagged parameters are not used for calculation of descriptive summaries, it will be footnoted in the PK parameters listing. For summarizing or calculating the summary PK parameters, the individual parameter values as provided by the Phoenix software will be used without any truncation.

In tables, figures, and listings, individual and summary  $C_{max}$  will be reported to the same precision as that provided by the Bioanalytical Lab,  $T_{max}$  will be reported in 3 decimal places in hours and all other PK parameters will be reported as 3 significant figures. N and n will be reported as whole number and CV% will be reported in 2 decimal places.

Box plots for  $C_{max}$ ,  $AUC_{last}$ , and  $AUC_{inf}$  and corresponding dose normalized parameters will be created to visually assess dose proportionality.

[figure not shown]
## 8.10.2.1 Assessment of Dose Proportionality

No formal dose proportionality assessment will be performed. Informal assessment of dose proportionality will be done using Box plots, displaying minimum, Q25, median (Q50), Q75 and maximum will be provided for NK-700  $C_{max}$  and AUCs by visit/day and dose level.

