# 2.2. SECONDARY

• Evaluate the PK of escalating doses of ANK-700 in patients with RRMS

2.3.

Study ANK-700-01 in Relapsing-Remitting Multiple Sclerosis

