# 3.2. SECONDARY ENDPOINT

• Plasma concentrations and PK parameters of ANK-700

Study ANK-700-01 in Relapsing-Remitting Multiple Sclerosis

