### 12.8. PHARMACOKINETIC ANALYSES

Blood samples will be collected for measurement of ANK-700, as specified in Table 1 and Table 2. The timing of sampling may be altered based on the emerging PK data. The adjustment of the PK sampling schedule is not considered to be a substantial amendment so long as the total number of plasma PK samples and the total blood volume to be collected from each participant will not change. Any adjusted sampling time points will be documented appropriately.

PK parameters of ANK-700 will be determined from the serum concentration-time data. Parameters will be calculated by noncompartmental modeling methods, using actual sampling times where relevant. The parameters that will be calculated are defined in Table 3 and will be calculated for single or multiple dosing of ANK-700, as appropriate. Not all listed parameters may be calculable, and additional parameters may be calculated, if needed, to fully characterize the available data. PK parameters and concentration data will be summarized for Part A and Part B and will be combined for doses with more than 2 patients in each dose group.

Anokion US, Inc.

**Table 5:** Pharmacokinetic Parameter Definitions

Parameter	Definition
$C_{max}$	Maximum observed plasma concentration
$T_{\text{max}}$	Time to first occurrence of maximum observed plasma concentration
C trough	Pre-dose plasma concentration
AUC last	Area under the plasma concentration-time curve from time 0 to the last measurable time point
AUC inf	Area under the plasma concentration-time curve extrapolated to infinity
AUC tau	Area under the plasma concentration-time curve over the dosing interval
t 1/2	Terminal elimination half-life
CL	Clearance
V z	Volume of distribution after a single dose
R acc,AUC	Accumulation ratio based on AUC
R acc,Cmax	Accumulation ratio based on C max

Statistical evaluations of PK data will include dose proportionality assessment using  $C_{max}$ ,  $AUC_{last}$ , and  $AUC_{inf}$ .

For cohort by cohort PK analysis, not all PK parameters may be calculated, and noncompartmental analysis may be done using nominal times.

Additional details on noncompartmental PK analyses for calculation of PK parameters and statistical analyses of PK parameters for dose proportionality will be provided in a PK analysis plan.

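### Protocol 12.8 includes dose proportionality in the statistical PK evaluation, but the SAP gives only box plots and does not list the change, so proportionality has no estimate with an interval

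*SAP*

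**What the plan says.** The secondary objective (Protocol 2.2) is "Evaluate the PK of escalating doses of ANK-700 in patients with RRMS", and the secondary endpoint (Protocol 3.2) is "Plasma concentrations and PK parameters of ANK-700". Neither names a proportionality slope.

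Protocol 12.8 states "Statistical evaluations of PK data will include dose proportionality assessment using" Cmax, AUClast and AUCinf. It names no model, interval or criterion. It says that details of "statistical analyses of PK parameters for dose proportionality will be provided in a PK analysis plan".

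SAP 8.10.2.1 says "No formal dose proportionality assessment will be performed" and describes an informal look at five-number box plots by day and dose. SAP 8.10.2 says that box plots of Cmax, AUClast, AUCinf and their dose-normalised versions "will be created to visually assess dose proportionality". No slope, ratio or interval is planned.

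The parameters themselves are summarised. Apart from tmax, SAP 8.10.2 says "For all other parameters N, n, mean, SD, CV%, median, minimum, maximum, geometric mean, and geometric CV% will be presented". Tables are planned by part and also for the pooled first dose: "Part A and Part B, Day 1 (combined), summary tables of ANK-700 calculable pharmacokinetic parameters will be provided". Clearance, defined in SAP 6.2 as dose divided by AUCinf, is among these parameters where it can be calculated.

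Protocol 12 lets the final SAP prevail where the two differ. SAP 1 says substantial differences will be identified in its Section 10, but that section covers data handling and missing data. SAP 12 lists no change and defers to the clinical study report.

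**The concern.** The study gives single doses over a 10-fold range, and its secondary objective is PK across escalating doses. Whether exposure rises in proportion to dose is a natural question for that objective, and the protocol names it as part of the statistical evaluation. The SAP answers it by eye.

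The visual answer is weakest at the top of the range. The 3.0 mg/kg dose is given only in Part A, to 3 patients unless the 3+3 rule expands the cohort to 6. A five-number box plot of 3 values shows little more than the 3 values. Protocol 1.4 allows data from both parts to support an amendment to higher doses, so a statement of how steeply exposure rises, and how uncertain that is, would have a use.

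The second issue is traceability. A reader of the SAP cannot tell that an evaluation named in the protocol was reduced to plots, or why.

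**Working it through.** The documents state no slope, precision, alpha or power for this question, so there is no planned figure to reproduce. The check asks how precise a slope the planned data would give.

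**Inputs from the documents.** Part A: 3 patients each at 0.3, 1.0 and 3.0 mg/kg (Protocol 4.1). Part B: 8 active patients each at 0.3 and 1.0 mg/kg (SAP 3.1). Pooled Day 1: 3 + 8 = 11, 3 + 8 = 11, and 3, so n = 25. All are taken as evaluable.

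**Assumed input.** The between-patient CV is not in the documents, so a range of 20% to 80% is used.

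**Model.** ln(parameter) = a + b ln(dose), where b = 1 is exact proportionality.

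- s = sqrt(ln(1 + CV²))
- SE(b) = s / sqrt(Sxx), with Sxx the sum of squares of ln(dose) about its mean
- 90% CI half-width = t(0.95, n − 2) × SE(b)

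**Sxx.** Mean ln(dose) = [11 × (−1.204) + 11 × 0 + 3 × 1.099] / 25 = −0.398. The contributions are 11 × 0.806² = 7.15 at 0.3 mg/kg, 11 × 0.398² = 1.74 at 1.0 mg/kg and 3 × 1.497² = 6.72 at 3.0 mg/kg. The total is 15.61. The 3 top-dose patients supply 6.72 / 15.61 = 43% of it.

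**Worked case, CV 30%.** s = sqrt(ln 1.09) = 0.294. SE(b) = 0.294 / sqrt(15.61) = 0.074. With 23 degrees of freedom, t = 1.714 and the half-width is 0.127. Over the 10-fold range that is a factor of 10^0.127 = 1.34 either way.

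| Assumed CV | Pooled Day 1 half-width | Factor over 10-fold | Pooled, with study-part term | Part A alone (n = 9) |
|---|---|---|---|---|
| 20% | 0.09 | 1.22 | 0.09 | 0.13 |
| 30% | 0.13 | 1.34 | 0.14 | 0.20 |
| 40% | 0.17 | 1.47 | 0.18 | 0.26 |
| 50% | 0.21 | 1.60 | 0.22 | 0.32 |
| 60% | 0.24 | 1.74 | 0.26 | 0.37 |
| 80% | 0.31 | 2.02 | 0.33 | 0.47 |

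Pooling narrows the Part A interval by about 35% (at CV 30%, 1 − 0.127/0.197). The study-part term costs little. If every Part A cohort expanded to 6 (n = 34), the pooled half-width at CV 30% would be 0.10.

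**Could the slope establish proportionality?** Take an assumed strict criterion of 0.80 to 1.25 across the 10-fold range. The limits for b are 1 ± ln(1.25)/ln(10) = 0.903 to 1.097. If b is exactly 1, the simulated chance that the pooled 90% CI lies wholly inside is about 20% at CV 20%, 0.4% at CV 30% and essentially nil from CV 40% upwards.

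**AUCinf.** Protocol 4.2 expects a half-life below 7 minutes. At 7 minutes, about 5% of the end-of-infusion level remains at 30 minutes (2^(−30/7) = 0.051) and about 0.3% at 1 hour. Some patients may therefore fail the terminal-phase rules in SAP 8.10.2 and have no summarised AUCinf. Cmax and AUClast are the safer parameters for the slope.

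**The case against.** The strongest case against is that this is largely preference in a small descriptive Phase 1 study.

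- A reader might infer that the secondary PK objective gets no estimate. It does: geometric means and geometric CV% are planned by dose for every parameter except tmax, including the pooled first dose. Dose-normalised box plots address proportionality directly, and clearance compared across doses is a rough numerical check.
- A reader might infer that the SAP breaches the protocol. The protocol promises no formal test, names no model, defers the method to a separate plan and lets the SAP prevail. The change is permitted; what is missing is its record in the SAP.
- The precision rests on an assumed CV, and the slope leans on the same 3 top-dose patients whose box plot is called weak. One atypical patient could move it, and three dose levels give little check of linearity on the log scale.
- Escalation within the study rests on Safety Monitoring Committee review of safety, tolerability and available PK, so a slope in the final analysis would not inform those decisions.

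All of this stands, and it limits the point. It does not remove it. Box plots carry no measure of uncertainty, whereas an interval shows openly how little 3 patients can say. An estimate with an interval is also compatible with a plan that tests no hypothesis.

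**Conclusion.** The point holds in a narrow form. The protocol places dose proportionality within the statistical evaluation of PK data, the SAP reduces it to visual assessment, and the SAP does not list the change. Only dose proportionality lacks an estimate with an interval.

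A descriptive slope on the pooled Day 1 data would have a 90% CI half-width of about 0.09 to 0.31 across assumed CVs of 20% to 80%. This assumes 11, 11 and 3 evaluable patients, a log-linear relation and no difference between parts (the study-part term tests the last of these). The tempting stronger reading is that the pooled data could show exposure to be dose-proportional. The working does not support it: even at CV 20% a strict criterion would be met only about one time in five.

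This is an inexpensive improvement, not a fault that threatens the study. Whether the PK analysis plan already contains the slope cannot be settled from these documents.

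**What to change.** In SAP 8.10.2.1:

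1. Add a descriptive power model, ln(parameter) = a + b ln(dose), on the pooled Part A and Part B Day 1 Cmax and AUClast, and on AUCinf where it meets the terminal-phase rules of SAP 8.10.2. Report b with a 90% CI and no pass/fail criterion.
2. Repeat each fit with a study-part term as a sensitivity analysis.
3. Keep the box plots and show the individual points on them.
4. If the PK analysis plan already specifies this, cross-refer to it instead of duplicating it.

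List the difference from Protocol 12.8 in SAP 12, and correct the reference in SAP 1 that points to Section 10. If the sponsor prefers plots alone, SAP 12 should say so and give the reason.

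The cost is two short regressions per parameter on data already being assembled, with no new samples or patients. The downside is a slope that draws about 43% of its information from the 3 patients at 3.0 mg/kg. The report should say so beside the estimate.

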## 8.10.2.2 Antidrug Antibodies

For Part B (MAD) only, immunogenicity summaries will be provided by treatment group on ATAS. Patients with any ADA positive samples, screening (ADA status) and confirmatory assay (titer, specificity, and ADA status) results will be included. The results for 3-Tiers will be displayed. If the sample is ADA-positive then the reactivity to the pgal and peptide will be included.

A by-subject listing of immunogenicity will be provided by study part and treatment group on enrolled patients.

#### 9. ADJUSTMENTS FOR COVARIATES

There will be no adjustment for covariates in this study.

#### 10. DATA HANDLING AND MISSING DATA

All missing or partial data will be presented in the patient data listing, as they are recorded on the eCRF. Patients lost to follow-up or withdrawn will be included in statistical analyses up to the point of their last evaluation.

## 10.1 Missing Start and Stop Dates/Time for Adverse Events

Due diligence will be done to obtain accurate AE information. If all planned methods to obtain accurate time AE information have failed, missing and partial AE onset and end dates will be imputed. Imputed dates will be flagged in the individual supportive patient listings. Unless otherwise specified, the following conventions will be used:

Missing and Partial AE onset dates:

- If onset date is completely missing, then onset date is set to date of first dose.
- If onset year is present and
  - month and day are missing:
    - If onset year = year of first dose, then set onset date to date of first dose.
    - If onset year < year of first dose, then set onset month and day to December 31st.
    - If onset year > year of first dose, then set onset month and day to January 1st.
  - month is missing:
    - If onset year = year of first dose, then set onset date to date of first dose.
    - If onset year < year of first dose, then set onset month to December.
    - If onset year > year of first dose, then set onset month to January.
- If onset month and year are present and day is missing:
  - If onset year = year of first dose and
    - onset month = month of first dose then set onset date to date of first dose.
    - onset month < month of first dose then set onset date to last day of month.
    - onset month > month of first dose then set onset date to 1st day of month.
  - If onset year < year of first dose, then set onset date to last day of month.
  - If onset year > year of first dose, then set onset date to 1st day of month.
- For all other cases, set onset date to date of first dose.

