#### 6.1.1 Adverse Events (AE)

An AE is defined as any untoward medical occurrence associated with the use of a drug, or with study participation, whether or not consider related to study treatment. An AE can

therefore be any unfavorable and unintended sign (eg, an abnormal laboratory finding), symptom, or disease temporally associated with the use of the medicinal product, whether or not considered related to the medicinal product.

AEs include worsening of a pre-existing medical condition, including MS, as well as Clinically Significant (CS) changes from baseline laboratory values/conditions. Worsening of the preexisting medical condition (eg, diabetes, hypertension) means that it has increased in severity, frequency, and/or duration, and/or has an association with a significantly worse outcome. A pre-existing condition that has not worsened during the study is not considered an AE.

All AEs are collected from the time of signing of Informed Consent Form (ICF) through the final Follow-Up Visit/phone. Adverse events will be coded using the Medical Dictionary for Regulatory Activities (MedDRA) Version 23.1 (MedDRA Sep 2020) or higher. Ongoing AEs considered at least possibly related to ANK-700 treatment should be followed until resolution, return to baseline, or are considered stable or chronic.

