## **6.1.2** Treatment Emergent Adverse Events (TEAE)

TEAEs are defined as AEs that emerge or worsen in the period from the first dose of study treatment to the final Follow-Up Visit/phone call after the last dose study drug. The incidence and severity of TEAEs as assessed by the CTCAE v5.0 or higher is considered the primary endpoint.

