#### 10.2 Missing Start and Stop Dates for Prior and concomitant Medication

For the purpose of inclusion in prior and/or concomitant medication tables, incomplete medication starts and stop dates will be imputed as follows:

- If year and month are present and day is missing, then set day to first day of month for start date and set day to last day of month for end date.
- If year and day are present and month is missing, then set month to January for start date, and set month to December for end date.

- If year is present and month and day are missing, then set month and day to January 1 for start date and set month and day to December 31 for end date.
- Completely missing date will not be imputed.

The partial dates will be provided as such in the patient data listings (with the imputed dates).

When imputing a start date, the programmer will ensure that the new imputed date is sensible i.e. it is before the end date of prior and concomitant medications.

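### SAP 10.1 can give a screening adverse event that ended before dosing an onset on the first-dose date, making it treatment-emergent, because the rule never consults the end date

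*SAP*

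**What the plan says.** SAP 10.1 applies once attempts to obtain the true date have failed. Its onset rules are:

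| Known part of the onset | Imputed onset |
|---|---|
| Nothing | "If onset date is completely missing, then onset date is set to date of first dose" |
| Month missing, with or without the day; year is that of first dose | "If onset year = year of first dose, then set onset date to date of first dose" |
| Only the day missing; month and year are those of first dose | "onset month = month of first dose then set onset date to date of first dose" |
| Only the day missing; same year, earlier month | "onset month < month of first dose then set onset date to last day of month" |
| Partial date in an earlier year | A date in that earlier year |
| Anything else | "For all other cases, set onset date to date of first dose" |

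None of these rules mentions the AE end date. The end-date rules in the same section are separate. They are anchored on the last dose and contain no comparison with onset.

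AEs are collected from consent (SAP 6.1.1, Protocol 6.1.15), and screening lasts up to 28 days (SAP 2.3.2, Protocol 4.2). SAP 6.1.2 states that "TEAEs are defined as AEs that emerge or worsen in the period from the first dose" and names TEAE incidence and severity as the primary endpoint.

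Medications are handled differently. When a start date is imputed, SAP 10.2 says "the programmer will ensure that the new imputed date is sensible i.e. it is before the end date". SAP 8.3 counts a medication with a missing start and a stop before first dose as prior.

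**The concern.** Setting an uncertain onset to the first dose is the usual cautious choice when nobody can tell whether an event began before or after dosing. A recorded end before first dose removes that doubt, because the event cannot have begun on treatment. SAP 10.1 applies the default all the same. The record then shows an onset later than its end, and so a negative value for the AE duration that SAP 8.8.1 says will be listed. Judged by its imputed onset, the event enters the TEAE tables rather than the Non-TEAE listing.

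At stake is the classification of events in the primary endpoint, in groups small enough for one patient to matter. The medication tables are protected against the same error; the primary endpoint is not.

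**Working it through.** The plan states no figure on this point, so there is none to reproduce. The check applies the rules as written.

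**Worked case.** First dose 24 June 2022; AE end recorded as 10 June 2022 (dates chosen for illustration).

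| Recorded onset | Imputed onset | After its own end? | TEAE by imputed onset? |
|---|---|---|---|
| Completely missing | 24 June 2022 | Yes, by 14 days | Yes |
| 2022 only | 24 June 2022 | Yes, by 14 days | Yes |
| 2022, day 5, month missing | 24 June 2022 | Yes, by 14 days | Yes |
| June 2022, day missing | 24 June 2022 | Yes, by 14 days | Yes |
| May 2022, day missing | 31 May 2022 | No | No |

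**Share of screening onsets that the rules move.** Assumptions: first dose is equally likely on any day of a 365-day year, and onset is equally likely on each of the 28 days before it.

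- Completely missing: 100%.
- Month missing: every onset is moved except those in the previous calendar year, which arise only with a January first dose. Over all pairs of first-dose date and onset in two such years (2 × 365 × 28 = 20,440), 19,628 are moved, or 96.0%.
- Only the day missing: an onset b days before dosing stays in the dosing month for (L − b) of the L possible dosing days in a month of L days. Summed over the 12 months, the share is (365 − 12b)/365. The mean of b over 1 to 28 is 14.5, so the share is 1 − 12 × 14.5/365 = 52.3% (10,696 of 20,440).

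The 52.3% covers all screening onsets. The defect also requires that the AE ended before dosing. For an AE lasting D days, b then runs from D + 1 to 28, with mean (D + 29)/2, and the share becomes 1 − 6(D + 29)/365:

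| Duration D (days) | Calculation | Share moved |
|---|---|---|
| 1 | 1 − 180/365 | 50.7% |
| 3 | 1 − 192/365 | 47.4% |
| 7 | 1 − 216/365 | 40.8% |
| 14 | 1 − 258/365 | 29.3% |

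These shares apply only to AEs whose onset day is still unknown after querying and whose end is known to precede dosing. The documents give no rate for that combination.

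**Effect of one such event.** Group sizes are 3 per Part A cohort, up to 6 if expanded (SAP 2.3.1), and 8 per Part B group, including pooled placebo (SAP 3.1). SAP 8.8 counts a patient once per event and once per system organ class. The any-TEAE percentage therefore moves only if the patient has no other TEAE. The shift is then 1/3 = 33.3 points, 1/6 = 16.7 points or 1/8 = 12.5 points.

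**The case against.** The best defence is that the SAP would expose such a record. Imputed dates are flagged and dates are listed as recorded (SAP 10 and 10.1), listings show onset, end and duration (SAP 8.8.1), and outputs are independently checked for consistency (SAP 8.1). With about 33 patients and no hypothesis test, a negative duration should be noticed. The rule also treats placebo and active patients alike in Part B. All of this lowers the chance that an error reaches the report. None of it states that the end date overrides the imputed onset in the tables, so a correction would rest on a programmer's judgement.

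A second defence is that an event over before dosing does not emerge or worsen on treatment, so the TEAE definition excludes it anyway. That is a fair reading of SAP 6.1.2. But SAP 10.1 supplies the onset date to which the definition is applied, and no rule settles the conflict.

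Third, the Part B schedules carry no AE mark at screening, while the Part A schedule does. The text of SAP 6.1.1 and Protocol 6.1.15 nevertheless requires collection from consent in both parts.

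Two stronger readings are tempting and are not supported:

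- A reader might infer that every partial onset is moved to first dose. Partial onsets in an earlier month or year are imputed to pre-dose dates and are unaffected.
- A reader might infer that a Grade 3 or higher screening event, redated into the dose-limiting toxicity window, could alter escalation. Those toxicities are reviewed by the Safety Monitoring Committee during the study (Protocol 4.6 and 4.9), and the SAP only lists them (SAP 8.8.1). Nothing says that imputed analysis dates feed those decisions.

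**Conclusion.** The point holds in a narrow form. Followed literally, SAP 10.1 gives a wrong result for a screening AE that has a recorded end before first dose and an onset that is completely missing, lacks the month in the year of first dose, lacks only the day in the month of first dose, or falls to the catch-all rule. The consequence is confined to the analysis tables and listings, but it touches the primary endpoint.

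The number of affected events cannot be derived from the documents and is probably small, since the rules apply only after queries fail. The 51% to 29% range rests on uniform dates and AE durations of 1 to 14 days. The shifts of 33, 17 and 12.5 points each assume one affected patient with no other TEAE. This should be corrected, but it does not undermine the design.

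**What to change.** Add to SAP 10.1, before database lock and unblinding:

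> If the recorded AE end date (complete, or partial but unambiguously before first dose) is before the first dose, the AE is not treatment-emergent, and a missing or partial onset that these rules would set to the first-dose date is instead set to the AE end date (for a partial end date, the latest date consistent with it that is before first dose). The first-dose default applies only when the end date is missing, ongoing, ambiguous, or on or after first dose.

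In the worked case, the four misclassified patterns then take 10 June 2022 as onset and become non-TEAEs. The cautious default remains wherever timing is truly uncertain. The cost is two sentences in the SAP and one programming check; no data collection changes.
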